7.2 Secondary Endpoints

Secondary endpoints will be evaluated at Weeks 2, 4, 8 and 12 unless otherwise stated.

- Percentage of subjects who would achieve ACR20, ACR50 and ACR70 response over time
- Change from baseline in DAS28-hsCRP score (based on 3 individual components including TJC, SJC, and hsCRP)
- Change from baseline in the tender/painful and swollen joint count (28)
- Change from baseline in the physician global assessment of disease activity by VAS
- Change from baseline in the subject global assessment of disease activity by VAS
- Change from baseline in the subject's assessment of arthritis pain by VAS
- Change from baseline in the HAQ-DI
- Change from baseline in median hsCRP values at each visit
- Safety and tolerability of SKI-O-703 compared to placebo including laboratory tests, infections, ECGs, vital signs, incidence of AEs, withdrawals due to AEs and serious adverse events (SAEs).
- PK parameters of SKI-O-592 and its metabolites (M2 and M4) from a subset of subjects per cohort on Day 1 and at Week 12, including: Cmax, Tmax, AUC0-tau, t1/2, Kel, CL/F (SKI-O-592 only), Vz/F (SKI-O-592 only), Rmet, and RAUC, as applicable
- PD parameters for the change from baseline in the percentage of activated gp53/CD63+ basophils in peripheral blood on Day 1 and at Week 12, including: Emax, TEmax, AUEC0-tau, as applicable

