7.7.4 Analysis of Secondary Endpoints

For secondary endpoints, change from baseline will be analyzed at Weeks 2, 4, 8, and 12 using a mixed model repeated measures (MMRM) analysis. The Chi-square tests will be used to compare the ACR20, ACR50, and ACR70 rates between the active treatment and placebo groups at Weeks 2, 4, 8, and 12. The median hsCRP will be summarized descriptively.

The DAS28-related secondary endpoint is based on 3 individual components including TJC, SJC and hsCRP (see calculation in Appendix 13.6). Sensitivity analyses based on the 4-component DAS28-hsCRP (consisting of 4 individual components including TJC, SJC, hsCRP, and subject's global assessment of disease activity [VAS]; see calculation in Appendix 13.6) will be performed using the ITT set restricted to subjects who consistently completed the subject's global assessment of disease activity reverse VAS scale.

All secondary endpoints will be analyzed using the ITT and PP analysis sets. The ACR20, ACR50, and ACR70 will be also analyzed using the mITT set, where results for subjects that are missing at the relevant visit will be imputed using nonresponder imputation (NRI).

For analyses on ACR responses (ACR20, ACR50 and ACR70) described above, the analysis will be performed on the subjects assessment of arthritis pain and physician global assessment of disease activity VAS scales, using the same approach as the sensitivity analysis on 4-component DAS28-hsCRP to identify the subjects to be included in this analysis set.

For the analyses on the other VAS-related secondary endpoints (ie, the individual assessments using VAS), using the same approach as the sensitivity analysis on 4-component DAS28-hsCRP, only subjects who completed the corresponding individual VAS assessment consistently will be included.

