2.2. Secondary Objective

The secondary objectives of this study are as follows:

- To evaluate the efficacy on other clinical endpoints of select (100 mg BID, 200 mg BID, and 400 mg BID) doses of SKI-O-703 compared with placebo in subjects with active RA who have had an inadequate response to csDMARDs or anti-TNF α biologic agents.
- To evaluate the safety and tolerability of select (100 mg BID, 200 mg BID, and 400 mg BID) doses of SKI-O-703 compared with placebo in subjects with active RA who have had an inadequate response to csDMARDs or anti-TNF α biologic agents.
- To investigate the PK profile of SKI-O-592 (the free base of SKI-O-703) and its metabolites (M2 and M4) in subjects with active RA who have had an inadequate response to csDMARDs or anti-TNF α biologic agents.
- To evaluate the effects of SKI-O-703 on exploratory PD biomarkers (i.e., the percentage of activated gp53/CD63 $+$ basophils in peripheral blood) in subjects with active RA who have had an inadequate response to csDMARDs or anti-TNF α biologic agents.

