3.2.2. Secondary Endpoints

The secondary efficacy endpoints will be evaluated at Week 2, 4, 8 and 12 unless otherwise stated.

- Percentage of subjects who would achieve American College of Rheumatology (ACR) response (ACR20, ACR50 and ACR70) over time
- Change from baseline in DAS28-hsCRP score (based on 3 individual components including TJC, SJC and hsCRP)

- Change from baseline in the tender/painful and swollen joint count (28)
- Change from baseline in the physician global assessment of disease activity by visual analog scale (VAS)
- Change from baseline in the subject global assessment of disease activity by VAS
- Change from baseline in the subject assessment of arthritis pain by VAS
- Change from baseline in the health assessment questionnaire - disability index (HAQ-DI)
- Change from baseline in median hsCRP values at each schedule visit
- Safety and tolerability of SKI-O-703 compared to placebo including laboratory tests, infections, ECGs, vital signs, incidence of AEs, withdrawals due to AEs and serious adverse events (SAEs).
- PK parameters of SKI-O-592 and its metabolites (M2 and M4) from a subset of subjects per cohort on Day 1 and at Week 12, including: C_{max} , T_{max} , AUC_{0-tau} , $t_{1/2,eff}$, R_{met} , and R_{AUC} , as applicable
- PD parameters for the change from baseline in the percentage of activated gp53/CD63+ basophils in peripheral blood on Day 1 and at Week 12, including: E_{max} , TE_{max} , $AUEC_{0-tau}$, as applicable

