7.3.2. Treatment Compliance

Treatment compliance (%) will be calculated for each subject as 100 times total dose divided by the intended total dose that should be taken over the treatment period. The intended total dose is calculated as 8 times the treatment duration. Compliance will be summarized using descriptive statistics by treatment group. The acceptable range for compliance is defined as between 80% - 120%. The number and percentage of subjects will be summarized by category $< 80\%$, $\geq 80\%$ to $\leq 120\%$, and $> 120\%$.

A subject data listing of study drug accountability will be provided, with the capsules dispensed, capsules returned, capsules taken, intended total dose and treatment compliance presented.

8. Efficacy Analysis

The primary analyses of all efficacy endpoints will be based on the ITT set, and then repeated using the PP set. The analyses of primary endpoint and secondary efficacy endpoints ACR20, ACR50 and ACR70 will also be provided based on the mITT set.

Each efficacy endpoint will be descriptively summarized by treatment group over time. In the summary for a post-baseline time point, subjects who have both values at baseline and at the time point will be included. Listings of all the efficacy endpoints will be provided by subjects.

Statistical comparisons will be performed between each of active treatment groups and the placebo group. All the statistical tests will be 2-sided and performed at a significance level of 0.05, leading to 95% CIs (2-sided). There will be no adjustment for multiplicity.

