8.1.1. DAS28-hsCRP

The DAS28 is a measure of disease activity in 28 joints and the core set of variables (individual components) for DAS28 for this study include:

- Number of tender joints with a total of 28 joints assessed for tenderness (TJC28)
- Number of swollen joints with a total of 28 joints assessed for swelling (SJC28)
- Subject global assessment for disease activity using VAS (PtGA)
- hsCRP (mg/L)

See details of the individual components in [Section 8.1.3](#), [Section 8.1.5](#) and [Section 1.7](#).

Unless otherwise specified, the DAS28-hsCRP mentioned in this document is based on 3 individual components (TJC28, SJC28 and hsCRP) and calculated using the following equation:

$$\text{DAS28-hsCRP(3)} = [0.56\sqrt{\text{TJC28}} + 0.28\sqrt{\text{SJC28}} + 0.36 \ln(\text{hsCRP} + 1)] \times 1.10 + 1.15,$$

where hsCRP must be in a unit of mg/L. High DAS28-hsCRP value indicates more severe disease activity.

Regarding 4-component DAS28-hsCRP analyzed in the sensitivity analysis, it is calculated using the following equation, consisting of 4 individual components (TJC28, SJC28, hsCRP and subject global assessment of disease activity):

$$\text{DAS28-hsCRP(4)} = 0.56\sqrt{\text{TJC28}} + 0.28\sqrt{\text{SJC28}} + 0.36 \ln(\text{hsCRP} + 1) + 0.014 \times \text{PtGA} + 0.96,$$

where hsCRP must be in a unit of mg/L and PtGA is in a scale of 0 - 100 mm where 0 represents very well and 100 represents not well.

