8.3. Secondary Efficacy Endpoints

8.3.1. Primary Analysis

The primary analysis will be conducted on observed cases without any imputation. All the secondary efficacy endpoints will be summarized and analyzed by treatment group at each schedule visit (Week 2, 4, 8, and 12) based on the ITT set and then repeated on the PP set.

The DAS28-related secondary endpoint is based on 3 individual components including TJC28, SJC28 and hsCRP (see calculation in [Section 8.1.1](#)). The analyses on ACR responses (ACR20, ACR50 and ACR70) will be restricted to subjects who completed subject global assessment of disease activity consistently, as well as physician global assessment of disease activity and subject assessment of arthritis pain, using the same approach as the sensitivity analysis on 4-component DAS28-hsCRP to identify the subjects to be included in the analysis. Similar to the

analyses on ACR responses, the analyses on the individual component using VAS will be restricted to subjects who completed the corresponding individual VAS assessment.

Frequency counts and percentages will be provided for ACR responses (ACR20, ACR50, and ACR70) at each schedule visit. The Chi-square tests will be used to compare the ACR response rate between each of active treatment group and placebo group, and among active treatment groups at each schedule visit. The p-values from the Chi-square tests will be presented. In case of few responders where Chi-square test may not be appropriate or accurate, Fisher's exact test will be performed instead. Besides, 95% CI of binomial proportion of ACR response within each treatment group and 95% CI of the difference in proportion of subjects with ACR response for pairwise treatment comparison will be estimated using the Wald method.

The hsCRP will be summarized descriptively by treatment group over schedule visits. No inferential statistics will be provided.

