For all other secondary efficacy endpoints, descriptive statistics of baseline, observed value and change from baseline at each schedule visit will be provided by treatment group. Treatment comparisons will be conducted using a mixed model repeated measure (MMRM) analysis, including all the scheduled visits up through Week 12. The model will be fitted with treatment group, visit, treatment by visit interaction and baseline as fixed effects, and visit within subject as a repeated effect, using an unstructured covariance to model the between- and within-subject errors. If the model fails to converge with unstructured covariance matrix, use the heterogeneous Toeplitz covariance structure, followed by the heterogeneous autoregressive covariance, followed by the compound symmetry covariance structure. The inferential statistics from this model, including within-group LS means and the associated SE, treatment differences in LS means and the associated SEs, the 2-sided 95% CIs, the 2-sided p-values for treatment comparisons between each of active treatment group and placebo, and the 2-sided p-values for treatment comparisons among different active treatment groups (high dose vs. low dose) will be provided.

Listings for ACR responses, DAS28-hsCRP assessments, number of tender and swollen joints, subject assessment of pain using VAS, subject and physician global assessment of disease activity and HAQ-DI will be provided.

Plots of LS mean change from baseline in continuous primary and secondary efficacy endpoints by visit will be provided as well. Proportion of subjects with ACR response will be plotted by visit.

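### hsCRP, a named secondary efficacy endpoint, gets no overall estimate, interval or test against placebo, while SAP 8.5 read literally would test it within subgroups on an unstated scale

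*SAP*

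**What the plan says.** SAP 3.2.2 lists among the secondary efficacy endpoints "Change from baseline in median hsCRP values at each schedule visit"; Protocol 7.2 has the same endpoint, "Change from baseline in median hsCRP values at each visit". The objective that these endpoints serve (SAP 2.2) is comparative: it sets the efficacy of the three doses against that of placebo. The opening of SAP Section 8 sets a general rule: "Statistical comparisons will be performed between each of active treatment groups and the placebo group".

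hsCRP is then taken out of that rule. Protocol 7.7.4 says "The median hsCRP will be summarized descriptively", and SAP 8.3.1 goes further: "The hsCRP will be summarized descriptively by treatment group over schedule visits. No inferential statistics will be provided". For the remaining continuous endpoints the same SAP section says "Treatment comparisons will be conducted using a mixed model repeated measure (MMRM) analysis, including all the scheduled visits up through Week 12", with LS mean differences, 95% CIs and p-values. The ACR rates get a Chi-square or Fisher test with intervals.

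Two other SAP statements do not repeat the exception. Section 8.5 covers all the secondary efficacy endpoints of 3.2.2 and, for those other than ACR, gives mixed-model treatment comparisons within each subgroup. Section 8.3.1 also promises plots of LS mean change by visit for the continuous primary and secondary efficacy endpoints.

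**The concern.** The trial takes a central-laboratory measurement at baseline and at Weeks 2, 4, 8 and 12, names it as an efficacy endpoint, and then declines to estimate the treatment effect on it. No reason is given.

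The omission falls on a useful variable. Protocol 6.3.1 reduced the primary endpoint to three components because the subject global VAS had been scored inconsistently across sites. Two of those components, the tender and swollen joint counts, rest on an assessor's judgement, and each is compared with placebo. The third, hsCRP, is the laboratory measure, and it is not. hsCRP is also untouched by the VAS problem that restricts the ACR and individual VAS analyses to consistently scored subjects.

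At stake is an estimate, with its uncertainty, of how far each dose lowers hsCRP relative to placebo, in a study whose results are meant to guide further clinical evaluation (Protocol 3.1.2). The text also leaves the programmer to guess whether the subgroup section and the LS mean plots include hsCRP, and on what scale.

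**Working it through.** **1. How each secondary efficacy endpoint is compared with placebo overall (SAP 8.3.1)**

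| Endpoint | Planned comparison |
|---|---|
| ACR20, ACR50, ACR70 | Chi-square or Fisher test, 95% CI of the difference |
| DAS28-hsCRP(3), joint counts, physician and subject global, pain, HAQ-DI | Mixed model: difference, 95% CI, p-value |
| hsCRP | None |

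Within subgroups (SAP 8.5) the second row's method covers everything except ACR, so hsCRP moves from no comparison to a mixed-model comparison. LS means for a plot also need a fitted model, and 8.3.1 fits none for hsCRP. No transform is stated for the model, so the default reading is the raw mg/L scale.

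**2. The plan's own figure.** There is no power statement for hsCRP. The only one is 37 completers per arm for DAS28-hsCRP (SAP 4.3: difference 0.8, SD 1.25, power 0.80, two-sided 0.05). Check: n = 2 × (1.960 + 0.842)² × 1.25² / 0.8² = 38.3, so 39 per arm. Power at 37 is 0.786 by the normal approximation and 0.806 for an overall four-group F test with one arm 0.8 away from the other three. The stated figure reproduces closely enough and is used below only as the available sample size.

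**3. What a log-scale comparison would give.** The SD and correlation are not in the documents. Assumed: SD of ln(hsCRP) 0.8 to 1.2, correlation r between baseline and follow-up 0 to 0.7.

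- SE = SD × √(1 − r²) × √(2/37), with √(2/37) = 0.2325
- Noncentrality = |ln(ratio)| / SE, two-sided t test on 72 df (critical value 1.993)
- Least favourable (SD 1.2, r 0): SE = 1.2 × 0.2325 = 0.279
- Middle (SD 1.0, r 0.5): SE = 0.866 × 0.2325 = 0.201
- Most favourable (SD 0.8, r 0.7): SE = 0.571 × 0.2325 = 0.133

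| True ratio to placebo | abs. ln(ratio) | Least favourable | Middle | Most favourable |
|---|---|---|---|---|
| 0.5 | 0.693 | 2.48 → 69% | 3.44 → 92% | 5.22 → 99.9% |
| 0.6 | 0.511 | 1.83 → 44% | 2.54 → 71% | 3.85 → 97% |
| 0.7 | 0.357 | 1.28 → 24% | 1.77 → 42% | 2.69 → 75% |

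(Cells show noncentrality → power.) The 95% CI is the estimated ratio multiplied and divided by exp(1.993 × SE): 1.30 in the most favourable case, 1.49 in the middle, 1.74 in the least favourable.

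**4. The scale matters.** Simulated baseline-adjusted comparison, 37 per arm, log-normal hsCRP, SD 1.0, r 0.5, true ratio 0.6, assumed median 8 mg/L: power is about 0.69 to 0.70 on ln(hsCRP), 0.68 to 0.69 on ln(hsCRP+1), and 0.48 on raw mg/L. With an assumed median of 15 mg/L it is 0.70 on ln(hsCRP) and 0.47 raw. Adding 1 before the log costs almost nothing; leaving the scale raw costs about 20 percentage points.

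Adding 1 does change what the ratio means. A fall from 10 to 5 mg/L gives (5+1)/(10+1) = 0.55, and from 2 to 1 gives 2/3 = 0.67, not 0.50. The result must be labelled as a ratio of (hsCRP+1).

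**5. Multiplicity.** Three doses × four visits = 12 further comparisons with placebo.

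**The case against.** The strongest reply is that this is a deliberate and consistent choice. Protocol and SAP both word the endpoint as a median and both make it descriptive, so there is no conflict between the two documents. The primary endpoint, sample size and type I error are untouched, and the plan already reports many unadjusted p-values. All of that stands. It limits the point's weight, but it does not supply the missing effect estimate that the stated objective calls for.

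Three stronger readings are tempting, and the documents do not support them.

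- A reader might infer that the trial can say nothing about hsCRP. By-arm summaries at each visit will include mean, SD, median and range (SAP 4.1), on subjects with both baseline and visit values (SAP Section 8), so an informal comparison is possible. hsCRP also enters DAS28-hsCRP and is one of the ACR items.
- A reader might infer that the log-scale model is already in the plan. It is not. The mixed model in 8.3.1 is for the other endpoints and states no transform. In the efficacy text the logarithm of hsCRP occurs only inside the DAS28 formula (SAP 8.1.1).
- A reader might put a figure on the information lost by working with medians. The SAP computes no between-arm contrast of medians and does not report medians alone, so no such figure describes this plan.

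On SAP 8.5 it can fairly be said that its reference back to 8.3.1 was meant to carry the hsCRP exception with it. That may be the intention, but the text names all secondary efficacy endpoints and excepts none, so it needs a sentence either way.

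**Conclusion.** The point holds as a cheap, worthwhile improvement to a secondary analysis. hsCRP is the only secondary efficacy endpoint without an overall estimate, interval or test against placebo, and SAP 8.5 and the LS mean plots do not fit the rule in 8.3.1.

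The size of the gain depends on assumptions. At 37 per arm, a log-scale comparison would probably detect a halving of hsCRP (about 69% to 99.9% power), has uncertain power for a ratio of 0.6 (44% to 97%), and is mostly underpowered for 0.7 (24% to 75%). These figures rest on an assumed SD of ln(hsCRP) of 0.8 to 1.2 and a correlation of 0 to 0.7. They are for a single visit on ln(hsCRP), and the simulation in step 4 suggests they carry over to ln(hsCRP+1) with little loss. Whatever the power, the interval would show what the data can and cannot exclude. The primary conclusion does not depend on any of this.

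**What to change.** In SAP 8.3.1, keep the descriptive medians and replace the sentence that rules out inference with the following:

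- Change from baseline in ln(hsCRP+1) is analysed with the mixed-model structure of 8.3.1, with baseline ln(hsCRP+1) as the covariate.
- Back-transformed ratios of (hsCRP+1) to placebo are reported with 95% CIs for each dose at Weeks 2, 4, 8 and 12, labelled as unadjusted for multiplicity.
- The same scale is used for hsCRP in SAP 8.5 and in the LS mean plots.

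Align Protocol 7.7.4, or record the departure in SAP Section 14, which now reports no changes. Do this before the SAP is finalised ahead of database lock.

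The cost is a few sentences and one additional model specification, run on data already collected, with no extra subjects or visits. The downside is one more set of unadjusted secondary comparisons (12 against placebo).

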4.3. Sample Size

Approximately 148 subjects will be enrolled in 4 cohorts (3 cohorts of SKI-O-703 and 1 cohort of placebo). Each cohort will consist of at least 37 subjects.

The study is powered to detect a difference of 0.8 in mean change from baseline to Week 12 in DAS28-hsCRP score between one of the groups treated with SKI-O-703 and the group treated with placebo. At least 37 subjects on a course of SKI-O-703 treatment are required to complete the study to show a change from baseline to Week 12 of 0.80 and higher as statistically significant with a power of 0.80 at the significance level of 0.05, using a 1-way analysis of variance and assuming a standard deviation of 1.25, compared with in the placebo group. Sample size determinations were based on the 4-component DAS28 and are likely to be similar with the 3-component DAS28 with fewer variables.

Given the 1:1:1:1 ratio of SKI-O-703 100 mg BID, 200 mg BID, 400 mg BID to placebo allocation, at least 37 subjects in each treatment group are required to complete the study, therefore at least 148 subjects need to be enrolled and randomized in the study. Assuming a drop-out of rate of 10%, up to 20 additional subjects may be enrolled to achieve the target number of subjects required to complete the study.

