8.2.1. Primary Analysis

The primary analysis will be conducted on observed cases, which means DAS28-hsCRP at Week 12 will be calculated only when all the three individual components (TJC28, SJC28 and hsCRP) are assessed at this visit; otherwise, DAS28-hsCRP at Week 12 will be considered as missing.

The change from baseline in DAS28-hsCRP at visit Week 12 will be analyzed using an analysis of covariance (ANCOVA) model. The model will include treatment groups as a factor and DAS28-hsCRP at baseline as a covariate. Within-group least-square (LS) means and the associated standard errors (SE), the treatment differences in LS means and the associated SEs, the 2-sided 95% CIs, the 2-sided p-values for treatment comparisons between each of active treatment group and placebo group, and the 2-sided p-values for treatment comparisons among active treatment groups (high dose vs. low dose) will be estimated and provided. Descriptive statistics of baseline, observed value and change from baseline at Week 12 will be summarized by treatment group.

The primary efficacy analyses will be performed based on the ITT set, and then repeated using the PP set.

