8.5. Subgroup Analysis

The focus of subgroup analysis will be limited to the baseline characteristics as listed below and the subgroup analysis will be conducted based on the ITT set for all the secondary efficacy endpoints specified in [Section 3.2.2](#). For VAS-related secondary endpoints (ACR responses and individual VAS assessments), the subgroup analysis will be restricted to subjects who completed the corresponding related VAS assessment consistently, same approach as described in the [Section 8.3.1](#) to identify the subjects to be included in the analyses.

- Number of previous csDMARDs treatments (0–2 csDMARDs, ≥ 3 csDMARDs)
- Previous anti-TNF α biologic agents use (Yes or No)
- Specific geographic region (APAC, EMEA, NA)

For ACR response endpoints, the number and percentage of responder and 95% Wald CIs will be provided by visit for each subgroup. The p-value of treatment comparison will be estimated by Chi-square tests within each subgroup. If all the subjects within a subgroup are responders or non-responders at a visit, only frequency counts and percentages will be provided for that subgroup and visit.

For other efficacy endpoints, the descriptive statistics of baseline, absolute value and change from baseline will be summarized by treatment group, scheduled visit and subgroup. By using the MMRM analysis as described in [Section 8.3.1](#), for each subgroup, the inferential statistics for treatment effect estimation and treatment comparisons will be provided by visit. In addition, subgroup comparison within treatment group will be provided as well by using a MMRM

analysis, which will be fitted with treatment group, subgroup, visit, treatment by visit interaction, treatment by subgroup interaction and baseline as fixed effects, and visit within subject as a repeated effect.

If too few subjects fall in the subgroup, the analysis within the subgroup may not be performed and only descriptive summary will be presented.

9. Safety Analysis

All the Safety analyses will be based on the Safety set.

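### The MMRMs for the secondary endpoints impose one baseline slope on all four visits; a baseline-by-visit term would be a cheap, modest improvement to the Week 12 contrasts.

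*SAP*

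**What the plan says.** SAP 8.3.1 gives the MMRM for the continuous secondary endpoints other than hsCRP, which is only described. The model statement is "The model will be fitted with treatment group, visit, treatment by visit interaction and baseline as fixed effects", with visit as the repeated effect, "using an unstructured covariance to model the between- and within-subject errors". Results are produced "at each schedule visit (Week 2, 4, 8, and 12) based on the ITT set".

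SAP 8.5 uses this model within each subgroup. It adds a second MMRM for comparing subgroups, whose terms end with "treatment by visit interaction, treatment by subgroup interaction and baseline as fixed effects". Neither model has a baseline-by-visit term. Protocol 7.7.4 says only that "change from baseline will be analyzed at Weeks 2, 4, 8, and 12 using a mixed model repeated measures (MMRM) analysis" and lists no covariates, so it does not supply the term either.

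The primary test is a different model. SAP 8.2.1 analyses Week 12 change in DAS28-hsCRP by ANCOVA: "The model will include treatment groups as a factor and DAS28-hsCRP at baseline as a covariate". That model uses Week 12 data only and so has its own Week 12 slope.

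**The concern.** The slope of change on baseline at visit t is cov(Y_t, Y_0)/var(Y_0) - 1. A single slope therefore requires baseline to covary equally with the Week 2 score and the Week 12 score. The same model leaves the covariances among the post-baseline visits completely free. Nothing in the documents supports the restriction on baseline, and a link to baseline that weakens over time would break it.

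What is at stake is the correction for chance imbalance. Randomisation is not stratified on baseline disease activity (Protocol 5.1, SAP 4.4), so the covariate does that work alone. The Week 12 contrasts for joint counts, VAS scores and HAQ-DI have only this MMRM. So do the subgroup DAS28-hsCRP contrasts, because SAP 8.5 limits subgroup analysis to the secondary endpoints and uses the MMRM for them. In the full ITT set, Week 12 DAS28-hsCRP is estimated twice, by ANCOVA and by MMRM, with different baseline adjustments.

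**Working it through.** **Inputs from the documents.** 37 per arm, SD 1.25 and a planning difference of 0.8 (SAP 4.3). Visits at Weeks 2, 4, 8 and 12. Baseline SD of the three-component DAS28 is 1.1 in the registry cited in Protocol 6.3.1. The plan gives no figure for this point, so there is none to reproduce. As a check on the planning inputs, 2 x (1.96 + 0.84)^2 x 1.25^2 / 0.8^2 gives 39 per arm against the stated 37, and power at 37 is 78.6%, which is close enough to use them.

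**Assumed.** Baseline SD 1.0. True slopes -0.10, -0.207, -0.313, -0.42 at the four visits. Residual SD at Week 12 of 1.25, either constant or rising to it in equal steps. Between-visit correlation as shown below.

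**Formulas.** With complete data:
- Week 12 contrast = raw difference - b_c x baseline difference between arms.
- b_c = sum of w_t x b_t, with weights w proportional to Sigma^-1 x 1, where Sigma is the residual covariance over the four visits.
- Shift for a 1-SD chance imbalance = |b_c - b_12| x SD_b x sqrt(2/37), and 1.0 x sqrt(2/37) = 0.232.
- SE ratio = sqrt(1 + (b_c - b_12)^2 x SD_b^2 / 1.25^2), ignoring the small cost of estimating the slope.

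**Results** (target Week 12 slope -0.42):

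| Residual SD | Correlation | Weights, Weeks 2 / 4 / 8 / 12 | b_c | Slope gap | 1-SD shift | SE |
|---|---|---|---|---|---|---|
| 1.25 constant | 0.6 per 4 weeks | 0.35 / 0.12 / 0.15 / 0.38 | -0.268 | 0.152 | 0.035 | +0.7% |
| 1.0 to 1.25 | 0.6 per 4 weeks | 0.54 / 0.06 / 0.13 / 0.27 | -0.221 | 0.199 | 0.046 | +1.3% |
| 0.8 to 1.25 | 0.6 per 4 weeks | 0.75 / -0.03 / 0.10 / 0.18 | -0.174 | 0.246 | 0.057 | +1.9% |
| 0.8 to 1.25 | 0.8 per 4 weeks | 1.20 / -0.31 / 0.01 / 0.10 | -0.102 | 0.318 | 0.074 | +3.2% |
| 0.8 to 1.25 | 0.7, equal | 0.86 / 0.31 / 0.01 / -0.17 | -0.080 | 0.340 | 0.079 | +3.6% |

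Third row in full: the gap is 0.42 - 0.174 = 0.246, the shift is 0.246 x 0.232 = 0.057, and the SE ratio is sqrt(1 + 0.0605/1.5625) = 1.019. One extreme combination goes beyond the table: SD rising from 0.8 with an equal correlation of 0.8 gives a shift of 0.095 and +5.2%. With constant slopes the gap is zero in every row.

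**Who sets the slope.** With equal residual SDs, Weeks 2 and 4 together carry 46-50% of the weight and Week 12 carries 25-43%. With SD rising from 1.0 the early pair carries 57-111%, and from 0.8 it carries 68-142%. Weights above 100% arise when visits are highly correlated and later ones more variable.

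**Simulation.** 37 per arm, 400 runs per setting, residual SD 0.8 to 1.25, about 9% missing at Week 12. The SE is the empirical SE of the Week 12 contrast.

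| True slopes | SE, common slope | SE, by visit | Power, common slope | Power, by visit |
|---|---|---|---|---|
| -0.15 to -0.45 (SD_b 1.0, corr. 0.6) | 0.303 | 0.295 | 0.74 | 0.765 |
| -0.10 to -0.60 (SD_b 1.1, corr. 0.7) | 0.312 | 0.296 | 0.74 | 0.77 |
| -0.30 at all visits (SD_b 1.0, corr. 0.6) | 0.288 | 0.290 | 0.725 | 0.73 |

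Average bias was 0.03 or less and coverage 94-96% in every setting. With 400 runs the Monte Carlo SE of one power figure is about sqrt(0.75 x 0.25/400) = 0.022, so the power differences indicate direction only. The SD of the difference between the two MMRM estimates was about 0.06 and 0.12 in the two settings with drifting slopes.

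**The case against.** The strongest reply is that a pre-specified common slope is a legitimate model for secondary endpoints, that its supposed fault depends on quantities the documents do not give, and that the effect is small. Most of that stands. Three stronger readings are tempting, and the documents do not support them.

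- A reader might infer that the early visits do determine the Week 12 adjustment. This needs residual variance that grows over time. With equal SDs the early visits do not dominate, and compound symmetry, the last covariance fallback in SAP 8.3.1, weights the visits equally. A slope gap can remain even so: equal weights on the assumed slopes give -0.26 against -0.42.
- A reader might infer that the Week 12 results are biased. Treatment is randomised, so the shift depends on the imbalance that happens to occur. It averages to about zero, and coverage holds.
- A reader might infer that the two Week 12 DAS28-hsCRP results contradict each other or that the primary result is at risk. SAP 8.2.1 identifies the ANCOVA as primary, and that model is untouched. With missing data the two would differ even with the added term, because the ANCOVA uses observed Week 12 cases and the MMRM uses all visits.

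The caution about subgroups also stands. With about 30% biologic-experienced (Protocol 3.1), such a subgroup has roughly 0.3 x 37 = 11 per arm, and three more parameters beside an unstructured covariance may make the fit unstable. SAP 8.5 already allows for subgroups too small to model.

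**Conclusion.** The restriction is real and unexplained, and its likely cost is modest. Under the stated assumptions a 1-SD chance imbalance moves the Week 12 DAS28-hsCRP contrast by about 0.04-0.08, against a planning difference of 0.8, and the SE rises by about 1-4%. In the third row of the table the shift is about a fifth of an SE (0.246/1.25 = 0.20). That ratio does not depend on sample size, so in a small subgroup the shift is larger in absolute terms, but so is the SE.

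The slopes, residual SDs and correlations are all assumed. The result scales with baseline SD and with the drift in slope, and vanishes if the slopes are constant. The figures are on the DAS28 scale; none were computed for joint counts, VAS scores or HAQ-DI, where the logic is the same but the size is unknown. The case for the change is that several Week 12 contrasts rest on this model alone and the remedy is nearly free.

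**What to change.** Add a baseline-by-visit interaction to the fixed effects of the MMRM in SAP 8.3.1. Carry it into both MMRMs in SAP 8.5 where the subgroup is large enough to fit the model, and state in advance whether the interaction or the unstructured covariance is given up first if a fit fails. Make the change before the SAP is finalised ahead of database lock.

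The cost is three parameters per model (four visit slopes in place of one), a small loss of precision if the slopes are in fact equal (empirical SE 0.290 against 0.288 in the simulation), and possible instability in small subgroups. With complete data and the unstructured covariance, the Week 12 DAS28-hsCRP estimate would then use the same baseline slope as the primary ANCOVA.
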